Hypothesis

The administration of guanfacine in ICU patients with delirium will reduce the duration of delirium.

Specific Aim

To quantify the duration of delirium in ICU patients treated with guanfacine or placebo.

Trial design

The study will be a prospective, single center, randomized, placebo-controlled, double- blind, intervention trial of guanfacine 2 mg versus placebo in critically ill patients admitted to the ICU with an expected LOS of at least 72 hours. (two arms, 1:1 enrollment, parallel design).

Methods

Inclusion criteria

- Patients admitted to the UAB hospital Surgical Intensive Care Unit (SICU)
- 18 years of age or older

- Expected total ICU length of stay of 72 hours or more per treating physician
- Diagnosed with delirium based on CAM-ICU assessment (see attached CAM-ICU assessment form)

Exclusion Criteria

- Patients younger than 18 years old
- Expected discharge from ICU within 72 hours of admission
- Expected or inevitable death with 48 hours of enrollment
- Pregnancy or breast feeding
- Non-English speaking
- Patients unable to be assessed by CAM-ICU due to neurologic illness
- Altered consciousness unable to participate in CAM-ICU assessment
- Patients with previous diagnosis of chronic, acute, subacute neurologic disease, or neurodegenerative disease
- Mental illness and/or psychosis
- Acute alcohol withdrawal
- No enteral route available for administration
- Treating physician refusal of enrollment based on severe hypotension (defined as requiring a vasopressor for longer than 24 hours) or bradycardia (Hr<50 bpm) at the time of screening
- Hepatic encephalopathy
- Blind or Hearing impaired
- Taking Guanfacine, for any reason
- On CYP3A inhibitor such as azole antifungals or clarithromycin
- On CYP3A inducers such as phenytoin or rifampin
- Severe xerostomia
- Enrolled in another interventional research trial

Intervention

-After patient or family member signs the informed consent

-Patients are enrolled within 48 hours of being diagnosed with delirium

-Randomization to placebo or study drug group on the day of enrollment

-Placebo group will receive pharmaceutical placebo.

-Guanfacine group will receive guanfacine 2 mg enterally via oral route or

nasogastric tube at 21:00 for 14 consecutive nights or until ICU discharge.

-CAM-ICU assessment will be conducted twice daily at am and pm. All data was deidentified and entered in secured RedCap database.

Outcomes

Primary

Duration of delirium

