The primary outcome will be the number of days alive without delirium during the 14-day treatment period after randomization. Delirium assessments are measured by the Confusion Assessment Method- Intensive Care Unit (CAM-ICU). CAM-ICU measures a patient's fluctuations in mental status, inattention, disorganized thinking, and consciousness.

All assessors using the CAM-ICU will receive training in the assessment tool along with monitoring to ensure the reliable implementation. The CAM-ICU will be used twice daily with all patients while admitted until ICU discharge. Patients will be diagnosed as delirious when they have at least one positive CAM-ICU on the day of assessment up to ICU discharge or day 14 after enrollment if remaining in ICU. Patients will be diagnosed as delirium free when they have four (4) negative consecutive CAM-ICU assessments. Assessors will be blinded to treatment group.

Secondary

1. Type of delirium or Coma

Based on patient RASS score, the participants will be categorized as having either hyperactive delirium (RASS >+1) or hypoactive delirium (RASS -3 to 0), Mixed (both hyperactive and hypoactive for the observation period), or Coma (RASS </= -4.

- 2. Duration of delirium Upon diagnosis of delirium, duration will be recorded as number of days of which the enrolled patient has a positive CAM-ICU until ICU discharge or day 14 after enrollment.
- Delirium Severity
 Assessors will administer the CAM-ICU-7 Delirium Severity assessment.
 Indirect markers of delirium severity will also be recorded daily until ICU discharge or day 14 after enrollment. These markers are: 1) need for anti-psychotics or sedation (total daily doses will be calculated); 2) need for physical restraints; 3) patient removal of intravenous lines, drains or catheters.
- 4. ICU and hospital LOS

Length of stay will be recorded using existing hospital data programs.

5. Morbidity and mortality

Markers of morbidity and mortality will be recorded on a daily basis until ICU discharge or day 14 after enrollment. These include: 1) duration of mechanical ventilation measured as ventilator free days; 2) daily need for vasopressor use; 3) daily need for renal replacement therapy; 4) reintubation, delayed extubation or need for tracheostomy; 5) SOFA scores; In addition we will record 6) mortality at 30 and 90 days; and 7) destination after ICU and hospital discharge.

Analysis

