Statistical Analysis. Demographics, such as gender, race, and age, as well as clinical characteristics (such as type of surgery, comorbidities) will be summarized using descriptive statistics. Continuous variables will be summarized using sample mean and sample variance whereas categorical variables will be summarized as proportions. The test of efficacy will follow the rejection region approach detailed in the Sample Size section using a Type I error rate of 0.05. 95% confidence intervals will be used to describe the incidence of delirium within the study population. Logistic regression models will examine whether age, gender, or comorbities associated with incidence of delirium when Guanfacine is administered.

Projected Sample Size. The primary outcome for statistical evaluation is delirium free days, defined as the number of days out of a 14-day period following enrollment. Power analyses are based on this outcome.

Based upon the historical evidence observed in the UAB Surgical ICU, delirium is experienced by approximately 24% of patients during their ICU stay.

All sample size and power estimates below assume a two-group, parallel design with 1:1 allocation ratio. In Table 1, we treat the primary outcome as number of delirium-free days during each patient's LOS.

We consider a range of detectable differences and desired levels of power in Table 1 below. The analysis consists of a two-sample t-test assuming equal variances and evaluation at a 0.05 level of significance. A mean difference of 10% is considered clinically meaningful, with larger differences indicating greater benefit. However, we do not have preliminary data providing reference values for the average and standard deviation of delirium free days in the control population. Thus, we express our detectable differences in terms of standard deviations between the two groups.

A sample size of 50 per group (100 total) will provide 85% power to detect an average proportion of delirium-free days in the treatment group that is at least 0.61 standard deviations different from the average proportion of delirium-free days in the control group.

Total(n)	Power	
	80%	85%
100	0.57	0.61
90	0.60	0.64
80	0.63	0.68

Table 1. Detectable Δ (standard deviation) with new sample size.

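### The plan estimates and models incidence of delirium in patients who were all enrolled with delirium, and gives that incidence no post-randomization definition

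*Combined protocol and SAP*

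**What the plan says.** The Inclusion criteria require that a patient be "Diagnosed with delirium based on CAM-ICU assessment". The Intervention section places enrollment after that diagnosis, by up to 48 hours. The Specific Aim is "To quantify the duration of delirium in ICU patients treated with guanfacine or placebo".

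The Statistical Analysis section then plans two analyses of incidence. The first is an interval estimate: "95% confidence intervals will be used to describe the incidence of delirium within the study population". The second, planned alongside that interval, is a regression with three kinds of covariate: "Logistic regression models will examine whether age, gender, or comorbities associated with incidence of delirium when Guanfacine is administered".

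Under Outcomes, Primary, there are two rules for classifying CAM-ICU results after enrollment. One works day by day: "Patients will be diagnosed as delirious when they have at least one positive CAM-ICU on the day of assessment". The other needs a run of results, which at two assessments a day spans about two days: "Patients will be diagnosed as delirium free when they have four (4) negative consecutive CAM-ICU assessments".

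Neither rule is linked to the incidence analyses, and incidence is not among the listed primary or secondary outcomes. The Projected Sample Size section says "The primary outcome for statistical evaluation is delirium free days", and powers the trial on that outcome.

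**The concern.** Incidence normally counts new cases among people free of the condition at the start. Here nobody is free of it at the start. Taken at face value, the confidence interval restates the eligibility criterion and the regression has an outcome that does not vary.

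The regression sentence also appears to confine the model to guanfacine recipients. If so, it uses about half of the patients and has no placebo patients to compare with. It then could not separate factors that predict outcome from factors that predict response to treatment.

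This is the only regression in the plan. To run it, someone must supply a binary outcome that the plan does not define, and nothing prevents that choice being made after the results are known. The only confidence interval the Statistical Analysis section names is spent on incidence; none is attached to the primary outcome.

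**Working it through.** **1. The plan's own figures.** The only figures available to reproduce are the detectable differences in Table 1. Inputs: two-sample t-test with equal variances, 1:1 allocation, alpha 0.05 (two-sided assumed, since sidedness is not stated). Noncentral t results, in SD:

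| Total n | 80% power: plan / recomputed | 85% power: plan / recomputed |
|---|---|---|
| 100 | 0.57 / 0.566 | 0.61 / 0.605 |
| 90 | 0.60 / 0.597 | 0.64 / 0.639 |
| 80 | 0.63 / 0.634 | 0.68 / 0.678 |

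All six cells agree. The sample size does not depend on the incidence analyses.

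**2. Literal reading, confidence interval.** By the inclusion criterion, x = n. The exact (Clopper-Pearson) lower 95% limit is then 0.025^(1/n):

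- n = 100: 0.025^(1/100) = 0.9638, so 96.4% to 100%.
- n = 50 (guanfacine arm): 0.025^(1/50) = 0.9289, so 92.9% to 100%.

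These limits depend on n alone. They cannot be set against the 24% in Projected Sample Size, which describes surgical ICU patients in general and not patients selected for delirium.

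**3. Literal reading, logistic model.** With all 50 outcomes equal to 1 and slopes at zero, the log-likelihood is −50 × ln(1 + e^(−a)) for intercept a:

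- a = 5: −0.336
- a = 10: −0.0023
- a = 20: −0.0000001

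It rises toward 0 without reaching a maximum, and does so for any fixed slopes, so the covariate effects are not identified. Numerical fits with a constant outcome and simulated age and gender gave separation or non-convergence warnings and standard errors from about 200 to over 100,000.

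**4. On-treatment readings.** Twice-daily assessment for 14 days gives 14 × 2 = 28 planned assessments. Two patient-level outcomes can be built from the rules under Outcomes, and neither is stated in the plan: (A) any positive CAM-ICU after enrollment is an event; (B) failing to reach four consecutive negatives is an event.

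| Patient | A | B |
|---|---|---|
| 1 positive, then 27 negatives | event | no event |
| 3 negatives, then ICU discharge | no event | event, unless early discharge is treated separately |

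The first patient is delirious on 1/14 = 7% of days under the daily rule. No event rates need be assumed to see that the definitions conflict.

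**5. Precision of the replacement.** Delirium-free days, 50 per arm, in SD units:

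- Mean per arm: t(0.975, 49)/√50 = 0.284.
- Between-arm difference: t(0.975, 98) × √(2/50) = 0.397.

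Covariate half-width = t/√(n·p·(1−p)), assuming three comorbidities, uncorrelated covariates and prevalence p:

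| Patients | p = 0.50 | p = 0.15 |
|---|---|---|
| Both arms, n = 100 (df 93) | 0.397 | 0.556 |
| Guanfacine only, n = 50 (df 44) | 0.570 | 0.798 |

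Treatment-by-covariate interaction with a balanced binary covariate (25 patients per cell): SE = √(4/25) = 0.4 SD. With df 96, the difference detectable with 80% power is about 1.13 SD.

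**The case against.** The best reply is that nobody would apply the literal reading. The regression sentence refers to the time when guanfacine is given, Outcomes supplies a daily rule that runs after enrollment, and enrollment can follow diagnosis by up to 48 hours, so the proportion positive after randomization could fall below 100%. This is a fair reading and may be what was meant. It shows that a repair exists, but the plan does not contain it: no rule, time window, relapse rule, or handling of death and discharge is tied to these analyses.

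A second reply is that the study population might loosely mean all screened surgical ICU patients, with 24% as the comparator. Nothing in the document supports that, and enrolled patients are the natural meaning.

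Several narrower points stand:

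- The conflicting definitions A and B are derived from the Outcomes rules. The plan does not offer them as rival endpoints, and its two rules do not contradict each other.
- Restriction to guanfacine recipients is the apparent meaning of a loose sentence, not a certain one.
- Defining a binary outcome would also cure the defect. The linear model asks a somewhat different question, and its treatment coefficient is a second efficacy estimate.
- Delirium-free days are bounded, so the normal-theory half-widths above are approximate.
- No efficacy conclusion depends on the two sentences.

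**Conclusion.** The concern holds. As written, both incidence analyses are degenerate for the enrolled population: the interval carries no information beyond the number enrolled, and the regression cannot be fitted. Under an on-treatment reading they become estimable only after an outcome is chosen that the plan leaves open, and that choice can change how a patient is classified.

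The literal result rests only on the inclusion criterion and the planned numbers, 100 in total and 50 per arm. The damage is confined to secondary analysis. The change should be made, and it is cheap, but it does not threaten the primary comparison.

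**What to change.** Replace both sentences in Statistical Analysis.

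1. Report mean delirium-free days in each arm and the between-arm difference, each with a 95% confidence interval, as the estimate that accompanies the primary t-test.
2. Replace the logistic model with one linear model of delirium-free days in both arms, containing treatment, age, gender and a short list of comorbidities fixed before unblinding. Label it exploratory and state that the t-test remains the test of efficacy.
3. Count days after death or ICU discharge exactly as in the primary analysis. That period must be settled first: Outcomes uses the 14 days after randomization, whereas for Table 1 the plan says "we treat the primary outcome as number of delirium-free days during each" patient's length of stay.
4. If a binary outcome is also wanted, define it before unblinding from the rule of four consecutive negatives, state how death, early ICU discharge and relapse are counted, label it exploratory, and report it with early discharge counted both ways.

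The cost is a change of wording and slightly more analysis, with data already planned. The adjusted treatment estimate concerns the primary outcome and adds no new endpoint. The drawback is imprecision: covariate intervals of about ±0.40 to ±0.56 SD at the assumed prevalences, though narrower than the ±0.57 to ±0.80 SD from guanfacine recipients alone. The main-effects model does not test predictors of treatment response. With an interaction detectable only at about 1.13 SD, none is proposed.

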Title: The Effect of Guanfacine on Delirium in Critically Ill Patients

Primary Investigator: [name]

University of Alabama at Birmingham Department of Anesthesiology and Perioperative Medicine, Division of Critical Care Medicine Contact: [contact]

[contact]

[name] is a full-time faculty member of the University of Alabama at Birmingham's Department of Anesthesiology and Perioperative Medicine and holds the academic standing of Associate [name] has basic science research experience and maintains a strong interest in medical education and clinical research.

NCT04578886

Date Aug 18, 2019

Location of Study: Research will be conducted at the University of Alabama at Birmingham Hospital and University of Alabama at Birmingham Highlands Hospital. Patients will be recruited in the UAB Surgical Intensive Care Units.

Abstract

Delirium has been identified as a significant problem in the intensive care unit that has been shown to lead to increased hospital and ICU length of stay, increased hospital cost, increased ventilator days, and long-term cognitive disability. The etiology of delirium is multifactorial, however, the elderly critically ill remain at highest risk. Therapy is largely targeted at nonpharmacologic prevention as promising treatments have not been standardized.

One such pharmaceutical treatment is the medication dexmedetomidine. Originally designed as an antihypertensive, dexmedetomidine is a central acting alpha agonist used as a sedation adjunct and has shown to reduce the duration of delirium in the intensive care setting. Guanfacine, a medication with the same mechanism and within the same class as dexmedetomidine, has a more specific sight of action in the frontal lobe and therefore more behavior modification properties. For this reason, guanfacine has been shown to be an effective adjunct therapy in Attention Deficit Hyperactive Disorder and has a secondary FDA approval for its use in that behavior disorder.

One of the hallmark symptoms of delirium is inattention and hyperactive behavior. Given the similarities between delirium and hyperactive disorders, guanfacine has been identified as a potential medication that may be of therapeutic benefit in the treatment of delirium. It is the purpose of this study to investigate the effects of guanfacine on delirium in critically ill patients admitted to the ICU.

Null Hypothesis

The administration of guanfacine in ICU patients with delirium will not reduce the duration of delirium.

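### The only covariate model appears to be limited to guanfacine-treated patients, so it cannot separate prognosis from effect modification and uses half the available data

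*Combined protocol and SAP*

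**What the plan says.** The design is randomised and placebo-controlled ("two arms, 1:1 enrollment, parallel design", Trial design). The efficacy analysis uses both arms: "The analysis consists of a two-sample t-test assuming equal variances and evaluation at a 0.05 level of significance" (Projected Sample Size).

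Covariates enter the plan in one sentence of the Statistical Analysis paragraph: "Logistic regression models will examine whether age, gender, or comorbities associated with incidence of delirium when Guanfacine is administered". The sentence just before it describes incidence for the study population as a whole, so the closing clause of the covariate sentence reads as a narrower condition. Nowhere do the documents give a treatment term for this model, a treatment-by-covariate interaction, a matching model in placebo patients, or a covariate-adjusted efficacy analysis. They also do not state in so many words that placebo patients are excluded.

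A positive CAM-ICU diagnosis of delirium is an inclusion criterion, so every participant already has delirium at enrolment.

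**The concern.** A covariate analysis in this trial could serve two purposes. One is prognosis: which patients do better or worse, whatever they receive. The other is effect modification: whether the benefit of guanfacine differs by age, gender or comorbidity. Benefit is a difference between arms, so the second question needs both arms and an interaction term. The first question does not need the second arm, but it is answered more precisely with it.

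A model in the guanfacine arm alone serves neither purpose well. A covariate with the same association in both arms and one that alters the drug's effect can give the same coefficient in that arm. A result framed as holding under guanfacine therefore invites a drug-specific interpretation that the model cannot support. Defining a usable outcome would not remove this problem, because the restriction to one arm would remain.

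**Working it through.** **1. The plan's own figure.** The covariate model has no stated power. The sample size does: "A sample size of 50 per group (100 total) will provide 85% power" for a difference of "at least 0.61 standard deviations different from the average proportion of delirium-free days in the control group", with the efficacy test run "using a Type I error rate of 0.05".

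- Normal approximation: 0.61 × √(50/2) − 1.96 = 3.05 − 1.96 = 1.09, which gives 86.2% power.
- Noncentral t, two-sided: 85.5%. A one-sided test would give 91.7%, which does not match.
- All six entries of Table 1 reproduce on the two-sided basis. The arm size of 50 is therefore sound as an input below.

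**2. Assumptions.** The plan states that "we do not have preliminary data providing reference values for the average and standard deviation of delirium free days in the control population", and it gives no binary event rate, covariate prevalence or covariate effect. I assume event rates p from 30% to 80%, a 50/50 binary covariate for the precision figures, 50 patients per arm, and two-sided 0.05.

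**3. Precision of each model.** For a 50/50 binary covariate in one arm of 50 (25 per level), the variance of the log odds ratio is v = 2 / [25 p(1 − p)]. Pooling both arms halves it to v/2. The interaction, a difference between two arms, has variance 2v. The effect detectable with 80% power is exp[(1.960 + 0.842) × SE].

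| p | One arm: SE, odds ratio | Both arms: SE, odds ratio | Interaction: SE, ratio of odds ratios |
|---|---|---|---|
| 0.5 | 0.566, 4.9 | 0.400, 3.1 | 0.800, 9.4 |
| 0.3 or 0.7 | 0.617, 5.6 | 0.436, 3.4 | 0.873, 11.5 |
| 0.8 | 0.707, 7.3 | 0.500, 4.1 | 1.000, 16.5 |

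For prognosis, the one-arm model has a standard error √2 ≈ 1.41 times that of the pooled model.

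**4. A purely prognostic covariate.** Simulated trials had 50 per arm, a 50% event rate, the same odds ratio in both arms and no true interaction. The share of trials with a significant result was:

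| Odds ratio per SD | One arm | Both arms pooled | Interaction |
|---|---|---|---|
| 1.5 | 27% | 49% | 4–5% |
| 2 | 60% | 89% | 4–5% |
| 2.5 | 79% | 98% | 4–5% |

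Repeat runs of the one-arm test gave 24–27%, 58–60% and 77–79%.

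For a yes/no covariate split 50/50 the SD is 0.5, so these per-SD odds ratios correspond to between-group odds ratios of 1.5² = 2.25, 2² = 4 and 2.5² = 6.25. A separate simulation with such a covariate gave one-arm significance in 24%, 45% and 63% of trials at between-group odds ratios of 2, 3 and 4. The interaction test stayed at about 5%.

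**5. Reading the two together.** The one-arm test responds to prognosis. The interaction test, which addresses the effect of guanfacine, stays at its nominal level. A significant one-arm coefficient therefore says nothing about whether guanfacine works differently across covariate levels.

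**The case against.** The wording is loose. It might mean a model that accounts for treatment, and no sentence excludes placebo patients. That stands: the one-arm reading is the natural one, not a stated restriction. If another model was meant, the sentence still does not describe it.

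Four stronger readings are tempting, and the documents do not support them.

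- *A reader might infer that the trial will report predictors of response to guanfacine.* The plan speaks only of association with incidence and never mentions responders or subgroups.
- *A reader might infer that the placebo arm is discarded.* At most it is left out of this one secondary model. The efficacy test compares both arms, and the incidence intervals cover the whole study population.
- *A reader might infer that an age association in the guanfacine arm is already expected, because the Abstract says* "the elderly critically ill remain at highest risk". That remark concerns the risk of having delirium. Participants are already delirious, and a risk factor for onset need not predict duration.
- *A reader might take the one-arm percentages as false-positive rates.* They are power to detect an association that was built into the simulation.

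It is also fair to say that an interaction test in 100 patients is weak, and that requiring one presumes an aim the plan does not state. For prognosis alone, a pooled model with a treatment term is enough. Finally, the sentence supports no stated hypothesis, specific aim or listed outcome, and it cannot be fitted until incidence is given a post-enrolment meaning. These points limit the severity. They do not make the one-arm model a good choice for either purpose.

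**Conclusion.** The point holds in a limited form. On its natural reading, the only covariate analysis is the wrong tool for effect modification and an inefficient one for prognosis. For prognosis, the odds ratio detectable with 80% power is 4.9 to 7.3 in one arm against 3.1 to 4.1 with both. For effect modification, a shared prognostic effect makes the one-arm model significant in roughly 25% to 80% of trials at odds ratios of 1.5 to 2.5 per SD, while the interaction test stays near 5%.

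The sizes rest on assumed event rates, covariate distributions and effects, because the documents give none. The logical point does not depend on them. The primary test and the sample size are untouched. Severity is minor to moderate.

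**What to change.** Replace the sentence, in the same edit that settles the undefined incidence outcome, with wording such as:

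> In all randomised patients, delirium-free days over the 14 days after enrolment will be modelled on treatment and one baseline covariate at a time (age, gender, and comorbidities named in advance), and the covariate association estimated from both arms will be reported. Where effect modification is of interest, the treatment-by-covariate interaction will be added and reported with a 95% confidence interval as exploratory. Associations within the guanfacine arm alone will not be interpreted as response to guanfacine.

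Delirium-free days is an example. A defined post-enrolment binary outcome with logistic regression would also serve.

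The cost is wording only: no new data and no change to the sample size or primary test. The downside is imprecise interaction estimates. For a binary outcome, the ratio of odds ratios detectable with 80% power is about 9.4 to 16.5 under the event rates assumed above. For delirium-free days with a 50/50 covariate and equal SDs, four cells of 25 give an interaction SE of √(4/25) = 0.4 SD. The detectable interaction is then 2.802 × 0.4 ≈ 1.12 SD, about twice the 0.57 SD that Table 1 gives for the treatment effect at 80% power. That is why the interactions should be labelled exploratory and reported as estimates with intervals.

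### The primary efficacy test is a valid but unadjusted t-test; prespecifying age as a covariate could gain a little precision at N = 100 for almost no cost

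*Combined protocol and SAP*

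**What the plan says.** The Statistical Analysis section hands the efficacy test to the sample size text: "The test of efficacy will follow the rejection region approach detailed in the Sample Size section using a Type I error rate of 0.05". The Projected Sample Size section then gives the test: "The analysis consists of a two-sample t-test assuming equal variances and evaluation at a 0.05 level of significance". Neither names a covariate, and the Methods describe no stratified randomisation.

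The primary endpoint is set under Outcomes, Primary: "The primary outcome will be the number of days alive without delirium during the 14-day treatment period after randomization".

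Age appears in four places:
- **Inclusion criteria.** Patients must be "18 years of age or older", so age is known for everyone before allocation.
- **Abstract.** "The etiology of delirium is multifactorial, however, the elderly critically ill remain at highest risk".
- **Statistical Analysis, descriptive part.** "Demographics, such as gender, race, and age, as well as clinical characteristics (such as type of surgery, comorbidities) will be summarized".
- **Statistical Analysis, last sentence.** Age is one of the predictors in logistic models for the incidence of delirium under guanfacine.

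It does not appear in the treatment comparison.

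**The concern.** In a randomised comparison of means, a baseline variable that predicts the outcome can be placed in the model to remove part of the residual variance. The plan considers age important enough to name as a risk factor and to model for delirium incidence, yet leaves it out of the one comparison that decides the trial. The logistic models do not fill the gap: they address a different outcome, and every enrolled patient already has delirium at entry.

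What is at stake is precision. With only 100 patients, a wider interval than necessary for the treatment difference is a real if modest loss. Choosing the covariate after unblinding would invite doubt, so the decision has to be made beforehand.

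**Working it through.** **Inputs from the documents.** 50 per arm, 1:1 allocation, alpha 0.05, equal-variance t-test, detectable differences in SD units (Table 1). Sidedness is not stated. Two-sided 0.05 reproduces Table 1, whereas one-sided 0.05 gives 0.501 and 0.540 SD at N = 100 against the tabulated 0.57 and 0.61. Two-sided is therefore used.

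**Input not in the documents.** R-squared, the share of outcome variance explained by age. It is assumed, and a range is shown.

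**Step 1: reproduce the plan.** Power is taken from the noncentral t with df = 98 and noncentrality δ·√(n/2), where δ is the difference in SDs. Solving for δ gives:

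| Total N | 80% power (plan) | 85% power (plan) |
|---|---|---|
| 100 | 0.566 (0.57) | 0.605 (0.61) |
| 90 | 0.597 (0.60) | 0.639 (0.64) |
| 80 | 0.634 (0.63) | 0.678 (0.68) |

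Table 1 is correct to rounding. At N = 100 and δ = 0.605, the noncentrality is 0.605 × √25 = 3.03 and power is 85.0%.

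**Step 2: add age.** One covariate takes df to 97, scales the residual SD by √(1 − R²), and costs a little for chance imbalance in age between arms (information factor 96/97). The noncentrality becomes

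0.605 × 5 × √[(96/97) / (1 − R²)].

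| Assumed R² | Noncentrality | Power | Detectable SD at 85% | Equivalent unadjusted N |
|---|---|---|---|---|
| 0 | 3.01 | 84.6% | 0.608 | 99 |
| 0.05 | 3.09 | 86.4% | 0.593 | 104 |
| 0.10 | 3.17 | 88.1% | 0.577 | 110 |

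Break-even is where (96/97) / (1 − R²) is about 1, that is, R² about 0.01.

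**Step 3: simulate with a normal outcome (20,000 trials per setting).** Unadjusted versus age-adjusted power with model-based errors was 85.1 vs 84.8% (R² 0), 85.1 vs 86.1% (0.05) and 85.3 vs 88.2% (0.10). This agrees with Step 2.

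**Step 4: simulate a bounded outcome (12,000 trials per cell).** Outcomes were whole days from 0 to 14 with an assumed 10% early deaths, and a control mean and SD of about 7 to 8 and 4 to 4.5 days (all assumed). The shift was set to 0.605 SD, and there were two settings.
- R² 0: 84.0 vs 83.2% and 83.5 vs 83.3%.
- R² about 0.03: 84.4 vs 85.3% and 83.7 vs 84.7%.
- R² 0.06 to 0.07: 84.5 vs 86.3% and 83.7 vs 85.5%.

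Type I error of the adjusted test was 4.8 to 5.2%. A separate check of the unadjusted t-test on five bounded 0 to 14 day shapes gave 4.9 to 5.1%. Both analyses hold their level.

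**The case against.** The strongest reply is that nothing here is broken. The t-test is valid under randomisation, it is prespecified, and its stated power reproduces. No stratification obliges adjustment. All of that stands, and a reader who infers that the planned test is wrong or biased goes beyond the documents.

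The second reply is that the prognostic premise is thin. The Abstract speaks of the risk of developing delirium, whereas the trial enrols only patients who already have it. Age may say much less about days free of delirium from then on. This stands too, and it is why the gain can only be called possible. A reader might also be drawn to larger benefits: at R² = 0.25 the same formula gives 93% power, equivalent to about 131 unadjusted patients. That would need a correlation of 0.5 between age and the outcome, which nothing in the documents supports.

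Third, the downside should not be understated. The formula gives a loss of 0.4 points when age is uninformative, but one bounded-outcome setting showed 0.8. The fair statement is 0.4 to 0.8.

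Fourth, other matters may weigh more, notably the base of the 10% difference. Read as 1.4 of 14 days, it matches 0.605 SD only if the SD is 1.4/0.605 = 2.3 days. At assumed SDs of 3, 4 and 5 days, unadjusted power for 1.4 days is 64%, 41% and 28%, and adjusting for age would not close that gap. A reader might infer that the trial is shown to be underpowered. It is not: both the reading of 10% and the SDs are assumptions, and the plan openly says it lacks a control mean and SD and therefore works in SD units. What remains is a wording clarification.

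**Conclusion.** The point holds as a modest, inexpensive improvement. Leaving age out of the primary comparison may give up about 1 to 3 points of power at N = 100, if age explains 5% to 10% of the variance in days alive without delirium. If it explains less than about 1%, adjustment loses slightly.

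The conclusion rests on an assumed R², a roughly linear age effect, and an outcome that is defined in one way. The last condition is not yet met. The sample size text describes the outcome as days out of 14, as days during the stay, and as a proportion, while under Outcomes, Primary, "The CAM-ICU will be used twice daily with all patients while admitted until ICU discharge". Adjusted or not, the test needs that settled.

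The case for acting is that the downside is small and bounded while the possible gain is somewhat larger. Confidence is medium, because the documents say nothing about how age relates to this outcome in patients already delirious.

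**What to change.** Before unblinding, amend the Statistical Analysis text as follows:
- The primary analysis is a linear model of days alive without delirium over 14 days on treatment group and age (continuous), with model-based standard errors, two-sided at 0.05.
- The adjusted treatment difference is reported with a 95% CI. The only interval now planned is for delirium incidence.
- The unadjusted two-sample t-test is kept as a sensitivity analysis.
- N stays at 100.

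Age should be the only covariate. The documents define no comorbidity score, and the inclusion criteria require admission to the surgical ICU, not an operation, so type of surgery may not apply to everyone.

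Two side clarifications belong in the same edit. State the 10% meaningful difference in days. Reconcile the three descriptions of the outcome with the primary outcome definition, including how days after ICU discharge count.

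Cost: SAP wording only, with no new data and no extra patients. The price is one degree of freedom and, if age is not prognostic, about 0.4 to 0.8 points of power.
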